### **5.2 SPECIFIC OBJECTIVES**

1. To design alternatives of Front of Pack Labels that are easy to understand and useful in guiding healthy food choices among Mexican consumers.
  - a. To explore how several nutrient profiling systems classify a sample of food products currently available in the Mexican market.
  - b. To explore the acceptability and understanding of Front of Pack Labelling Systems used in the international food market in a sample of Mexican consumers living in urban areas.
  - c. To identify the graphic and language elements of the labelling systems that facilitate the understanding of the message of the labels towards healthy food selection.
  - d. To design Front of Pack labeling proposals considering the graphic and language elements identified in the previous step.
2. To identify which of the proposed labels has the best performance, in terms of acceptability and objective understanding, in a sample of Mexican consumers.

- a. To explore the acceptability and understanding of Front of Pack Labelling Systems used in the international food market in a sample of Mexican consumers living in urban areas.
3. To evaluate the efficacy of the two best labelling proposals to promote healthy food choices using an on-line shopping simulation in a sample of Mexican consumers.

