## 6 HYPOTHESIS

---

A front of pack labelling system that takes into account the graphic and language elements considered by Mexican consumers as relevant for communicating the “healthy” message, will be effective in improving the nutritional quality of food choices during an on-line shopping simulation in this population.

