### **7.3.1 Design of the study**

Three-arm randomized controlled trial without blinding

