### **7.3.4 Intervention**

The intervention will consist on an on-line purchase simulation with different labelling systems on food products. Participants will be randomly assigned to one of the three conditions using a randomization program: Control group, (no front-of-pack labeling), Label Proposal 1, and Label Proposal 2. Due to the nature of the intervention there will be no blinding of the intervention.

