### 7.3.6 Analysis of the Data

The impact of the two label proposals will be evaluated using a linear regression model, where the outcome will be the mean nutritional quality of the products bought, whereas the independent variable will be the intervention group. The model will be adjusted for the main demographic confounders such as age, sex, civil status, having children and educational attainment and chronic disease. Differences will be considered statistically significant when  $p < 0.05$ . Analysis will be carried out using STATA version 14.0.

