### 7.3.7 Sample size

Based on previous experiences [46], and considering a significance level of 0.05 and a statistical power of 80%, at least 273 participants per intervention group will be required to detect a difference of 0.3 points in the mean nutritional quality between intervention groups (Figure 7).

**Figura 7.** Tamaño de muestra necesario para detectar una diferencia mínima en nutricional.

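### Do two label-versus-control comparisons at p<0.05, with no stated joint test, order or adjustment, require a multiplicity rule?

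*Combined protocol and SAP*

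**What the plan says.** Section 7.3.1 describes a "Three-arm randomized controlled trial without blinding". Section 7.3.4 names the arms: "Control group, (no front-of-pack labeling), Label Proposal 1, and Label Proposal 2". In section 7.3.6, "The impact of the two label proposals will be evaluated using a linear regression model", with mean nutritional quality as the outcome, intervention group as the independent variable and adjustment for demographic factors. The decision rule is a single sentence: "Differences will be considered statistically significant when" p<0.05.

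Two places bear on what counts as success. Section 6 predicts that a label built on elements that consumers find relevant "will be effective in improving the nutritional quality of food choices during an on-line shopping simulation in this population". Objective 3 in section 5.2 is "To evaluate the efficacy of the two best labelling proposals to promote healthy food choices using an on-line shopping simulation".

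Section 7.3.7 says that "at least 273 participants per intervention group will be required to detect a difference of 0.3 points", at significance level 0.05 and 80% power. It does not say which pair of groups this refers to, or whether the test is one- or two-sided. No section lists contrasts or mentions a joint test of group, a testing order or an adjustment.

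**The concern.** A three-level group variable has no single coefficient, so the regression yields at least two label-versus-control estimates. The plan does not say how they combine into a conclusion. Section 6 is worded in the singular, so a success for either label could be presented as confirming it. With two chances at 5% each, the chance of a false finding somewhere exceeds 5%. If Proposal 1 versus Proposal 2 were also tested, there would be three chances. The results are meant to inform labelling policy, so a false claim for one label would matter. A stated rule looks like an inexpensive safeguard, because the joint test comes from the model already planned.

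**Working it through.** **Inputs from the documents.** Three arms (7.3.1, 7.3.4); p<0.05 (7.3.6); difference 0.3 points, level 0.05, power 80%, 273 per arm (7.3.7).

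**Assumptions.** Two-sided tests and equal allocation, neither of which is stated. The SD is not in the readable text (Figure 7 is not visible), so it is back-solved. Covariates are ignored.

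**1. The plan's own figure.** With n = 2(1.960 + 0.842)² SD² / 0.3², setting n = 273 gives SD = 0.3 × √(273/2) / 2.802 = 1.25. Putting SD 1.25 back in gives 272.5, so 273. The figure fits one two-group comparison at two-sided 0.05 with no adjustment. This shows consistency only, since the SD was derived from it. A one-sided 0.05 test would imply SD 1.41, and a two-sided 0.025 test about 1.14.

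**2. Error rates when neither label works.** Each contrast has variance 2σ²/n. The shared control gives covariance σ²/n, so the correlation is 0.5. None of these rates depends on the SD.

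- Any false difference over two contrasts: 1 − P(|Z1|<1.96, |Z2|<1.96) = 0.0907. Treating the contrasts as independent would give 1 − 0.95² = 0.0975.
- False improvement for at least one label: 1 − P(Z1<1.96, Z2<1.96) = 0.0454, against 0.025 for one two-sided test.
- If the tests were one-sided at 0.05: 1 − P(Z1<1.645, Z2<1.645) = 0.088, against 0.05.
- All three pairwise comparisons, two-sided and ungated (studentized range): 0.122.

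**3. The same tests under the other readings.**

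- *Each label is its own question.* Each answer has a 5% error rate, which is what section 7.3.6 states.
- *Both labels must succeed.* With neither working, the chance that both tests reject is 0.05 + 0.05 − 0.0907 = 0.0093. If one label works and the other does not, it is at most 0.05.

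Only the either-label reading inflates the error.

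**4. What a rule would cost.** Simulation, 2,000,000 trials per scenario, 273 per arm, SD 1.25. The gate is the 2-df F test at 0.05 followed by two-sided 0.05 contrasts. Step-down Dunnett uses 2.212, then 1.96.

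| | No rule | Joint-test gate | Step-down Dunnett |
|---|---|---|---|
| Any false difference, two control contrasts | 9.1% | 4.2% | 5.0% |
| False improvement claim | 4.5% | 2.1% | 2.5% |
| Power per 0.3 contrast, both labels work | 80% | 76% | 77% |
| Same, other label has no effect | 80% | 76% | 72% |
| Same, other label halfway (0.15) | 80% | 70% | 73% |
| At least one label found, both work | 91% | 83% | 86% |

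At SD 1.14 the gate takes power per contrast from 87% to 84% (78% with the other label halfway). At SD 1.41 it takes it from 70% to 64% (58% halfway).

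Restoring 80% with single-step Dunnett (per-test level about 0.027) needs about 324 per arm, which is 3 × (324 − 273) = 153 more participants. Bonferroni needs about 331 per arm, or 3 × (331 − 273) = 174 more.

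**The case for a change.** The strongest case for a change is that section 6 is the only formal hypothesis, that it is singular, and that nothing prevents a reader from treating one success out of two as confirmation. Stating the rule before data are seen would settle this under every reading and needs no extra participants. With exactly three groups, the joint-test gate followed by unadjusted contrasts is a closed test, so it holds familywise error at 5% or less even if label versus label is added.

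Much of this stands. The arithmetic is right, no rule appears anywhere in the documents, and a sentence naming the two control contrasts would help a reader. What does not follow is that an adjustment is owed. Section 6 describes a kind of label and sets no rule that either one is enough. Objective 3 asks about two distinct proposals, and leaving different interventions with a shared control unadjusted is a recognised position. A joint test of group is neither written nor excluded. The 9% also counts a label falsely found to worsen choices, whereas the hypothesis concerns improvement, for which the two-sided figure is 4.5%. Finally, a gate at 273 per arm would leave section 7.3.7 quoting 80% power for a rule no longer in use.

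**Conclusion.** No change to the plan is needed. Section 7.3.6 is brief, but its test is not wrong and it breaks no promise of its own, because familywise control is never claimed. On the either-label reading, with two-sided ungated tests and equal arms, the error rates are about 9.1% for any false difference and 4.5% for a false improvement claim. On the separate-questions or both-labels reading there is no inflation. Familywise control would cost about 3 to 10 points of power per contrast at the assumed SD of 1.25, or at least 153 more participants to restore 80% with single-step Dunnett. That is a trade-off on which reasonable statisticians differ. The gap closes in ordinary practice: report both label-versus-control estimates with confidence intervals, judge each label on its own result, and treat any label-versus-label comparison as additional. The conclusion would change only if the trial were to claim success on the strength of whichever label reached p<0.05.

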### 7.3.7 Sample size

Based on previous experiences [46], and considering a significance level of 0.05 and a statistical power of 80%, at least 273 participants per intervention group will be required to detect a difference of 0.3 points in the mean nutritional quality between intervention groups (Figure 7).

**Figura 7.** Tamaño de muestra necesario para detectar una diferencia mínima en nutricional.

## 8 ETHICAL CONSIDERATIONS

This research proposal will be carried out considering the guidelines established by the Institutional Research, Ethics and Biosecurity Boards.

A written consent will be requested from all participants for the participation in focus groups, questionnaires and purchase simulations. Participants will receive a copy of the consent form with contact information of the head of the Ethics Committee, in case they have any questions or concerns regarding the project.

Each participant will be assigned an identification number that is not related to any personal information. Information collected as part of the research will remain confidential and it will only be known by the researchers. All field and digital records of focus groups will be kept in the office of the principal investigator, and access will be restricted to researchers of this study only. Audio files will be destroyed once transcriptions and data analysis are completed.

This study will not collect human biochemical samples in any of its three components, it does not imply any biosecurity risks for participants. Regarding ethical aspects, we consider

the proposal implies minimum risks for the participants, since the participants will provide their consent. At all times ethical principles of fieldwork will be respected: informed consent, autonomy and freedom to refuse to participate in the project.

## **9 LIMITATIONS**

---

The sample for the three stages will not be representative of the Mexican population. Therefore, external validity of the results could be limited to people with similar characteristics of the sample. Nevertheless, previous experiences in Mexico show that understanding and acceptability of the different FoPNL alternatives does not differ by socioeconomic levels. We consider that the information collected will provide relevant information for the design and conduction of future studies in the topic of Front of Pack Labelling.

The use of online tools could have a low response rate, limiting the sample size and consequently statistical power to find differences. However, we have considered hiring an expert company in online market segmentation for the dissemination of the online shopping simulation, as well as through websites with a high traffic of users. By reaching a higher number of individuals we will have a better chance of meeting the required sample size.

The current study will not evaluate the effectiveness of the labelling proposal in a real environment. Therefore, results can only be interpreted as purchase intentions. The evaluation of effectiveness of a FoPNL in a real environment has political, logistic and economic implications that go beyond the scope of this Project.

